A randomized placebo-controlled, cross-over pilot study in which 20 adults with type 2 diabetes will participate in two experimental trials. All participants will provide written informed consent during an initial familiarization visit.

Following screening, eligible participants (N=20) will participate in two experimental trials of β -OHB supplementation versus placebo with order of treatment balanced, separated by ~7 days. Pre-menopausal women will be tested in the follicular phase (days 3-9) to minimize any potential changes in insulin sensitivity across the menstrual cycle [8]. Participants will be asked to refrain from structured exercise and alcohol, and limit physical activity to their activities of daily living on the day before each trial. A standardized diet with ~50% energy from carbohydrate, ~30% fat, ~20% protein (energy based on Harris-Benedict equation with an activity factor of 1.4) will be oriented on the day before each trial. Participants will then fast overnight (8-10h) and refrain from taking any medications 24 hours before the morning of the trial. Upon arrival, an indwelling intravenous catheter will be inserted and a baseline fasting blood sample will be obtained. The oral β -OHB supplement or placebo will be consumed in liquid form (~20-25 mL). Both drinks are masked with a proprietary calorie-free strawberry flavour developed by H.V.M.N®, USA, which results in the same taste profile for each. The β -OHB supplement will provide 0.3 g/kg β -OHB in the form of the ketone monoester (*R*)-3-hydroxybutyl (*R*)-3-hydroxybutyrate (Δ G®, TDeltaS, Oxford, UK). We used this dose in our supporting pilot study and published work shows it can consistently raise blood β -OHB levels to ~2-3 mmol/L within 15-30 minute[9] [2] [10]. Post consumption of the β -OHB or placebo blood samples will be obtained at 30, 60, 90, 120, 150 and 180 minutes.

The primary outcomes will be total plasma glucose as represented by the 3-hour area under the curve. Secondary outcomes include plasma insulin and C-peptide levels, plasma free fatty acids (FFA), inflammatory cytokines, cerebral blood flow (CBF), cognitive function, BDNF, signalling molecules, self reported hunger and fullness by a Visual Analog Scale (VAS) and GI symptom questionnaire scores – all measured across 180 minutes post-supplementation.

Metabolite and hormone analyses

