Experimental Trial A (duration 210 minutes)

Females will complete experimental trials in the follicular phase. Participants will report to the laboratory after an overnight fast (8-10 hours). Adherence to the 24 hour diet will be confirmed upon arrival in the laboratory, as well as information about physical activity and sleep. An indwelling intravenous catheter will be inserted into the antecubital vein for repeated blood sampling by a trained phlebotomist ([name] and [name]). Blood (5 ml) will be drawn into EDTA tubes for measurement of plasma samples before being frozen in a -80 degree Celsius research refrigerator. There will be 7 intravenous blood draws in total for a total of ~35 ml of blood collected in each trial. The first collection will occur prior (0) to consumption of ketone or placebo drink. Another 6 blood draws will occur at 30 minute intervals (30, 60, 90, 120, 150, 180) after ingestion of the ketone or placebo drink. Thirty minutes after ingestion, participants will be instructed to complete the gastrointestinal distress questionnaire. Brain blood flow and blood pressure will be measured non-invasively and a cognitive test battery will be performed in separate intervals throughout the study. During the visit participants will answer a brief questionnaire regarding satiety and hunger. Subjects will be reminded to not perform exercise or to consume alcohol or medications 24 hours prior to the next visit.

Protocol timeline

Visit 2: Experimental Trial B

Subjects will return fasted to the laboratory at least 2 days after the first visit. Adherence to the 24 hour diet will be confirmed upon arrival in the laboratory. Participants will be instructed to identify any deviations in diet before beginning the second trial. Protocol for the second visit will be the same as visit 1, although participants will receive the remaining condition (ketone supplementation or placebo).

Statistical Analyses

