Descriptive statistics (means, SD, and frequencies) will be calculated and Q-Q plots of residuals used to test for normality and skewness. Significance will be set at $P<0.05$. Data with a time component will be analyzed using a linear mixed effects model with subjects as a random factor and condition and time as fixed factors using SAS. Main effects of condition and condition X time interactions will be probed with planned comparisons to examine differences between β -OHB and placebo at each time point. Data with skewed distributions will be log-transformed or non-linear mixed effects models will be used. All participants will be included in the intention-to-treat (ITT) analyses and missing data will not be imputed, per contemporary guidelines with use of linear mixed models [16].

Sample Size

Twenty participants will be included in this cross-over study. In our pilot study on healthy volunteers we saw a ~15% reduction in glucose area under the curve after

ketone supplementation versus placebo. Using means and standard deviations from our previously published study in people with T2D (N=51) [17] for fasting glucose (8.6 +/- 2.3) a 15% reduction in blood glucose corresponds to an effect size $d = 0.73$. Assuming 80% power with an alpha level of 0.05 and a moderate correlation between repeated measures of $r=0.7$ (calculated using G*Power v3.1) a total sample size of $n=14$ is needed to detect differences between ketone and placebo conditions. To preserve power and account for any dropouts or missing blood samples we will recruit 20 participants, aiming for equal males and females.[2][17]

Significance

The results of this study will help determine whether supplementation with exogenous ketones can alter metabolism and subsequently improve blood glucose levels. This is a pilot study and it will provide useful data to better answer future research questions and aid in the design of longer term studies.

OUTCOMES MEASUREMENTS AND METHODS

The primary outcome measure is the plasma glucose concentrations over the 3-hour period following the ingestion of the beverages. Secondary measures will include plasma insulin and C-peptide, free fatty acids, inflammatory cytokines, CBF, cognitive function and neurovascular coupling, inflammation signalling molecules, appetite/satiety levels and gastrointestinal distress questionnaire.

Anthropometric Measures

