The full analysis set of data will be derived from the set of all randomized participants in an intention-to-treat (ITT) analysis. All outliers that are within the realm of biological plausibility will be included in the analysis and only obvious data errors (e.g., resulting from technical issues) will be excluded. No statistical imputations will replace missing data for the outcome measures (*data as observed*), per contemporary guidelines [3]. However, the linear mixed effects model (see below for further details) is a principled approach to addressing missing outcome data. The model permits the inclusion of all participants in the analysis with a follow-up value (regardless of missing timepoints within a condition, or a missing alternative condition). Statistical analysis will be performed blinded to participant allocation.

OUTCOMES, STATISTICAL METHODS, AND COVARIATES

Primary endpoint: The preregistered primary outcome for this trial will be a comparison of blood glucose values assessed over 180 minutes following consumption of exogenous ketones or a placebo. Data will be analyzed according to the ITT principle via a linear mixed effects model with fixed effects for time after supplement ingestion (i.e., 30, 60, 90, 120, 150, 180 minutes), condition (i.e., ketone monoester vs placebo), period (depending on which condition was conducted first), and an interaction between time and condition and time and period as well as the baseline value (assessed at “time 0” immediately before consumption of the supplement) as a covariate. A random intercept for each participant (ID) and a random slope for time on the interaction of ID and period will be included. If a participant has a baseline value missing, we will impute this as the average (mean) baseline value observed across participants. Model assumptions of normality and linearity will be assessed visually by inspecting a Q-Q plot, and homoscedasticity will be assessed by plotting residuals vs fitted values. Models will be run using log-transformed outcome variables when departure from model assumptions is observed.

In addition to the primary analysis detailed above, we will explore the primary endpoint via the following confirmatory analyses:

1. Paired t-test on blood glucose incremental area under the curve (i.e., glucose above baseline fasting values across 180 minutes after ingestion of supplement or placebo)

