2. Paired t-test on peak blood glucose concentration (i.e., highest blood glucose value measured after ingestion of supplement or placebo)
3. Paired t-test on peak blood glucose concentration above baseline (i.e., highest blood glucose value above fasting baseline after ingestion of supplement or placebo)
4. Paired t-test on blood glucose total area under the curve (i.e., glucose above zero across 180 minutes after ingestion of supplement or placebo)

Secondary outcome measures:

Secondary outcomes will be analyzed similarly to the primary outcome using a linear mixed effects model. Secondary and exploratory blood marker outcomes that are below or above the detection limit, will be imputed as limit of detection (LOD) / $\sqrt{2}$ or $LOD * \sqrt{2}$, respectively [4]. Preregistered secondary outcomes include:

1. Metabolic outcomes (plasma insulin, plasma c-peptide, plasma free fatty acids, plasma β -OHB)
2. Markers of brain/cognitive function (intracranial blood flow measured by ultrasound, blood pressure measured manually, cognitive function using BrainBaseline on an iPad, brain-derived neurotrophic factor)
3. Markers of inflammation (plasma tumour necrosis factor alpha, plasma interleukin-1 β , plasma interleukin-6, total blood monocytes and monocyte subsets, monocyte histone acetylation)
4. Markers of appetite (self-reported hunger and fullness assessed via a 0 to 100 mm Visual Analog Scale, gastrointestinal symptoms assessed via a 0 to 100 mm Visual Analog Scale, total energy consumed in kilocalories during a buffet style meal at the end of testing)

Exploratory outcomes measures:

Exploratory outcomes will be analyzed similarly to the primary outcome using a linear mixed effects model.

Exploratory outcomes that were not preregistered include:

1. Metabolomics
2. Electrolyte status, lactate, pH etc.

REPORTING RESULTS

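### Should the supplementary paired t-tests on total AUC and peak glucose adjust for each visit's time-0 glucose?

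*SAP*

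**What the plan says.** The SAP's Primary endpoint section fits a linear mixed model to glucose at 30 to 180 minutes. It has terms for condition, time, period, time-by-condition and time-by-period, and it includes the time-0 value, taken "immediately before consumption of the supplement) as a covariate". The Reporting Results section commits to the condition effect, its interaction with time, and covariate-adjusted mean differences with 95% confidence intervals.

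Four paired t-tests follow, introduced by "In addition to the primary analysis detailed above, we will explore the primary endpoint via the following confirmatory analyses":

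- Analysis 1 uses the "incremental area under the curve (i.e., glucose above baseline fasting values across 180 minutes".
- Analysis 2 is a "Paired t-test on peak blood glucose concentration (i.e., highest blood glucose value measured after ingestion of supplement or placebo".
- Analysis 3 uses the peak above fasting baseline.
- Analysis 4 is a "Paired t-test on blood glucose total area under the curve (i.e., glucose above zero across 180 minutes after ingestion of supplement or placebo".

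Analyses 2 and 4 carry no baseline term. The sample is available at both visits. The protocol's Experimental Trial A section says "The first collection will occur prior (0) to consumption of ketone or placebo drink", and the second visit follows the same procedure.

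The protocol words its primary outcome in two ways. Experimental design has "The primary outcomes will be total plasma glucose as represented by the 3-hour area under the curve". Outcomes Measurements and Methods has "The primary outcome measure is the plasma glucose concentrations over the 3-hour period following the ingestion of the beverages".

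**The concern.** A fasting sample is drawn before each drink and is a covariate in the main model, yet the two raw-value t-tests ignore it. Analyses 1 and 3 use it only by subtraction, which fixes the slope at 1 instead of estimating it (for analysis 1, only if area below baseline is counted). So no listed stand-alone AUC or peak analysis estimates the baseline slope.

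If a person's fasting difference between visits predicts the later difference well, the intervals for total AUC and peak will be wider than the data allow. This seems to matter more because one protocol section names the 3-hour AUC as primary, and analysis 4 is the SAP's only direct test of total AUC.

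**Working it through.** **Inputs.** From the sample-size sections of both documents: mean fasting glucose 8.6, SD 2.3 mmol/L, 15% reduction, correlation 0.7 between conditions, N = 14 needed, 20 to be recruited. From the SAP's Reporting Results: two-sided 0.05. Not in the documents, so assumed over a range:
- rho, the within-person correlation between the visit difference in time-0 glucose and the visit difference in outcome;
- k, the SD of the baseline difference divided by the SD of the outcome difference.

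**The plan's own figure.** Effect = 0.15 × 8.6 = 1.29. SD of the paired difference = 2.3 × √(2 × (1 − 0.7)) = 1.78. Ratio = 1.29 / 1.78 = 0.724, close to the stated 0.73. A paired t-test with 0.73 gives N = 14 at one-sided 0.05 (power 82.7%). At two-sided 0.05 it needs 17. That mismatch is a separate matter and does not bear on this point. Two-sided power is used below.

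**Is the unadjusted test biased?** No. Order is randomised and balanced, so a chance difference in fasting glucose between visits is part of the sampling variation that the t-test's standard error already measures. Only precision is in question.

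**Size for a stand-alone test.** The alternative is a regression of the within-person outcome difference on the time-0 difference and sequence. Its residual SD is 1.78 × √(1 − rho²), with N − 3 degrees of freedom, averaged over the chance baseline differences. Total AUC is expressed as a 3-hour mean.

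| | Unadjusted | rho 0 | rho 0.3 | rho 0.5 | rho 0.7 |
|---|---|---|---|---|---|
| Power, N = 20 | 86.7% | 84.1% | 87.3% | 92.6% | 98.4% |
| CI width relative to unadjusted, N = 20 | 1 | 1.04 | 0.99 | 0.90 | 0.74 |
| Power, 14 pairs | 70.7% | 65.7% | 69.7% | 77.7% | 90.7% |
| CI width relative to unadjusted, 14 pairs | 1 | 1.06 | 1.01 | 0.92 | 0.76 |

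The mean unadjusted width is 1.65 mmol/L at N = 20 and 2.02 with 14 pairs. Break-even rho is about 0.27 and 0.33. Below that, the t-test as written is the better test.

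**Total AUC: does the plan already give an adjusted answer?** With samples every 30 minutes, the trapezoid AUC divided by 180 puts weight 15/180 = 1/12 on time 0, 30/180 = 1/6 on each of 30 to 150 minutes, and 1/12 on 180 minutes. The condition effect averaged over the six post-drink samples puts 1/6 on each. Once the time-0 difference is held at zero, its 1/12 drops out. The two adjusted effects then differ only in the weight on the 180-minute value (1/12 against 1/6). In 64 simulated settings (four effect profiles, two drifts, two residual SDs, four values of rho), the two adjusted effects correlated at 0.9986 or higher.

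**Peak: what is left to gain?** Analyses 2 and 3 are the unadjusted and the subtracted versions. The variance of the subtracted version relative to the unadjusted one is 1 + k² − 2k·rho, so subtraction wins when rho exceeds k/2. Regression gains most over the better of the two at rho = k/2. With equal SDs (k = 1) that is rho = 0.5, where both existing tests have relative SE 1 and the regression interval is 0.90 as wide at N = 20, so 10% narrower. At rho = 0.7, subtraction gives √(2 × 0.3) = 0.775 against 0.74 for regression, about 5% narrower. At k = 0.8 the largest gain is 1.04 × √(1 − 0.4²) = 0.95. At k = 1.25 it is 1.04 × √(1 − 0.625²) = 0.81.

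**The case for a change.** The strongest case for acting is that the change is cheap: one sentence, a few lines of code and no new data. The loss is bounded at a 4 to 6% wider interval if baseline is uninformative, and the interval could be about a quarter narrower at rho = 0.7. After an overnight fast, 3-hour glucose may well track the fasting value. The SAP calls these tests confirmatory, and one protocol section makes AUC primary. The mixed model's condition effect is not a peak difference. If the model is run on the log scale, which the SAP allows, its effect is not an arithmetic AUC difference either. The mixed model also estimates its baseline slope from all participants' visits, so its adjusted figure will be close to the within-person regression but not identical.

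These statements are correct, and some stand. Peak has no analysis with an estimated slope, and the SAP does not say whether incremental AUC counts area below baseline. The latter is a missing definition, not a fault in analyses 2 and 4. The two wordings of the primary outcome are likewise a separate question.

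None of this makes the t-tests wrong. The benefit rests on a correlation nobody can read from the documents, and its sign changes within the plausible range. Adding regressions while keeping the t-tests would turn four supplementary tests into six, each at 0.05. The peak regression would also need a rule for missing time-0 values that analysis 2 does not need. The SAP states that the trial was completed by November 2021 and carries adjustments up to April 2022. The documents give no unblinding date, so an addition might have to be labelled post hoc.

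**Conclusion.** The concern does not hold. Analyses 2 and 4 are valid, unbiased and supplementary, and the primary model beside them already adjusts for time-0 glucose and period. For total AUC, an adjusted test would nearly duplicate a result the plan reports. For peak with equal SDs, it would be at most about 10% narrower at N = 20 than the better of the two tests already listed. That figure depends on the SD ratio: about 5% at k = 0.8 and 19% at k = 1.25.

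The stand-alone figures, from a 4% wider to a 26% narrower interval at N = 20, rest on assumed rho from 0 to 0.7. They also reuse the plan's fasting-glucose SD and correlation for a 3-hour mean, because the documents give no SD for AUC or peak. Whatever rho is, the trial's primary conclusion does not change. Choosing simple unadjusted summaries to accompany an adjusted model is a defensible trade-off.

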We will summarize data (including participant baseline characteristics) as mean \pm standard deviation (SD) for continuous and N (%) for categorical data. A significant effect will be concluded at two-sided P -value of < 0.05 . We will report on the effect of condition and the interaction of the treatment effect over time. Effect estimates from the model alongside 95% confidence intervals around the mean differences in the outcome after accounting for the included covariates will be reported. Changes in outcome within condition (e.g., effect of ketone monoester on blood glucose at 180 minutes compared to baseline) will be reported via mean differences with SD outside the model, if applicable. Effect sizes (Hedges' g) will be stated.

PROGRAMMING PLAN

Statistical analysis will be performed after the last patient out, using R [5].

REFERENCES

1. Myette-Côté, É., et al., Prior ingestion of exogenous ketone monoester attenuates the glycaemic response to an oral glucose tolerance test in healthy young individuals. *The Journal of Physiology*, 2018. **596**(8): p. 1385-1395.
2. Francois, M.E., et al., Combined interval training and post-exercise nutrition in type 2 diabetes: a randomized control trial. *Frontiers in Physiology*, 2017. **8**: p. 528.
3. Chakraborty H. A mixed model approach for intent-to-treat analysis in longitudinal clinical trials with missing values [Internet]. 2009. Available at: <http://www.rti.org/publication/mixed-model->

approach-intent-treat-analysis-longitudinal-clinical-trials-missing-values

4. Canales R.A., et al. Methods for handling left-censored data in quantitative microbial risk assessment. *Appl Environ Microbiol* 2018. **84**(20): e01203-18.
5. Team RC. A Language and Environment for Statistical Computing. R Foundation for Statistical Computing 2020. Available at (accessed November 4, 2021): <https://www.r-project.org/>
- 6.

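### A single baseline coefficient blends between-person and within-person slopes, so secondary and exploratory ketone contrasts can lose precision without becoming biased

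*SAP*

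**What the plan says.** The SAP's primary-endpoint model has fixed effects for time, condition and period, plus "an interaction between time and condition and time and period as well as the baseline value", which is the pre-drink value of the visit. Its random part reads: "A random intercept for each participant (ID) and a random slope for time on the interaction of ID and period will be included". Under Secondary outcome measures: "Secondary outcomes will be analyzed similarly to the primary outcome using a linear mixed effects model". The exploratory outcomes get the same instruction. If a baseline is missing, "we will impute this as the average (mean) baseline value observed across participants". Participants with only one condition stay in the analysis.

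Neither document adds a participant-mean baseline or centres baseline within person. The model in the Protocol's Statistical Analyses section has no baseline covariate at all. The SAP's paired t-tests, which use no shared baseline slope, are planned for glucose only.

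The Protocol (Experimental design; Experimental Trial A) documents a time-0 blood draw at each visit, "with order of treatment balanced". It does not fix a pre-drink assessment for the cognitive battery or the hunger and satiety ratings. It places the gastrointestinal questionnaire 30 minutes after the drink. The buffet meal in the SAP is measured once, at the end.

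**The concern.** Each participant brings two baselines, and these hold two kinds of information. One is between-person: people with high values tend to stay high. The other is within-person: whether a value that is high today, for that person, predicts higher values later today. With a random participant intercept and one baseline coefficient, the fitted coefficient falls between the two slopes.

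The ketone–placebo contrast compares a person with himself or herself, so only the within-person slope is relevant to adjusting it. If the blended coefficient is larger than the within-person slope, the adjustment over-corrects and adds noise. What is at stake is the width of the confidence intervals for secondary and exploratory outcomes in a trial of 20 people.

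**Working it through.** **Inputs.** From the documents: 20 participants, two visits, six post-drink times, the SAP's fixed and random effects, and baseline SD 2.3 with r = 0.7 (SAP, Sample size considerations; these were given for glucose). Assumed, because the documents give nothing: both baseline slopes and all residual variances. The plan states no figure for the precision of baseline adjustment, so there is none to reproduce.

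**Step 1: cost of a wrong coefficient.** Let g be the fitted coefficient minus the within-person slope, Vw the within-person baseline variance, and Vr the visit-level residual variance of the time-averaged outcome. The between-visit difference, adjusted with the fitted coefficient, has variance inflated by

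ratio = 1 + g² × Vw / Vr.

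Example: Vw = (1 − 0.7) × 2.3² = 1.587, visit SD 0.5 and sampling SD 0.5 averaged over six times, so Vr = 0.25 + 0.25/6 = 0.292. With g = 0.25, the ratio is 1 + 0.0625 × 1.587/0.292 = 1.34. In SD terms, split over single is 1/√1.34 = 0.86, before the small price of estimating a second slope.

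**Step 2: why the slopes usually differ.** Write a value as person (Vp) + visit (Vd) + sample noise (Ve), with the visit part persisting through the visit. Then

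- within slope = Vd/(Vd + Ve), with odds Vd/Ve;
- between slope = (Vp + Vd/2)/(Vp + Vd/2 + Ve/2), with odds (2Vp + Vd)/Ve.

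The odds differ by 2Vp/Ve. Under this structure the within slope is the smaller one whenever people differ and the baseline reading is noisy.

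**Step 3: simulation with slopes set directly.** 20 people, between slope 1, REML, 150 data sets per row. Columns 3 to 5 use the SAP's random terms as written. SD is the empirical SD of the ketone contrast.

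| Within slope | Participant / visit SD | Fitted single slope | SD single / split | Split ÷ single | Same ratio with added visit intercept |
|---|---|---|---|---|---|
| 1.0 | 0.5 / 0.5 | 1.00 | 0.161 / 0.163 | 1.01 | 1.01 |
| 0.8 | 0.5 / 0.5 | 0.88 | 0.169 / 0.172 | 1.02 | 0.99 |
| 0.5 | 0.5 / 0.5 | 0.75 | 0.200 / 0.179 | 0.90 | 0.82 |
| 0.2 | 0.5 / 0.5 | 0.60 | 0.213 / 0.163 | 0.77 | 0.64 |
| 0.5 | 1.5 / 1.0 | 0.65 | 0.348 / 0.341 | 0.98 | 0.93 |
| 0.2 | 1.5 / 1.0 | 0.37 | 0.311 / 0.304 | 0.98 | 0.85 |

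The fitted coefficient lies between the two slopes, as expected. The third row has g = 0.75 − 0.50 = 0.25 and gives 0.90, against 0.86 from Step 1. The largest mean error of the contrast was 0.048, with a simulation error of 0.311/√150 = 0.025. Each SD carries about 6% simulation error (1/√(2 × 149) = 0.058), so differences of a few percent mean little.

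Empirical SDs are used because, with the random terms as written, the model SE was too small when visits differed in level (first row: 0.126 against 0.161). That is a separate matter, and splitting the baseline does not cure it (0.127 against 0.163).

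**Step 4: simulation from variance components.** Here the slopes follow from Step 2. Total variance 1, Vp = 0.7, 150 data sets per row.

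| Vd / Ve | Within / between slope | Split ÷ single, as written | With added visit intercept |
|---|---|---|---|
| 0 / 0.30 | 0 / 0.82 | 0.79 | 0.60 |
| 0.10 / 0.20 | 0.33 / 0.88 | 0.89 | 0.87 |
| 0.15 / 0.15 | 0.50 / 0.91 | 0.98 | 0.89 |
| 0.25 / 0.05 | 0.83 / 0.97 | 1.02 | 1.02 |

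Further runs of this kind with 100 data sets, terms as written, gave 1.00 at slopes 0.50/0.91, 1.00 at 0.50/0.83, 0.92 at 0.20/0.73 and 0.995 at 0.14/0.54. Another series with 200 data sets per setting gave 0.75–0.97 as written and 0.66–0.99 with a visit intercept.

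**Step 5: scale.** At a ratio of 0.90, the single-slope analysis of 20 people is worth a split analysis of 20 × 0.90² = 16.2. At 0.75 it is worth 20 × 0.75² = 11.3.

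**The case against.** A per-visit baseline covariate with a random participant intercept is ordinary covariance adjustment, and the SAP states it clearly. A reader might infer that the ketone effect is biased. It is not: baseline precedes the drink and treatment order is randomised and balanced. The simulations show no clear bias, and in a visit-mean version (1,500 data sets per setting) type I error was 4–7% with either form of adjustment.

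A reader might also infer a definite percentage loss. The documents do not support one. The slopes and residual variances are assumed, and SD 2.3 and r = 0.7 belong to the glucose sample-size argument, not to cytokines or cognition. The larger gains need a visit-level random intercept that the SAP, read literally, does not include. Nor does a noisy measure lose much automatically: noise lowers the between-person slope too, and at slopes 0.14/0.54 the gain was only 0.5%.

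Finally, a reader might apply the point to every secondary outcome, but a time-0 value at both visits is documented only for the blood draws.

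All of this limits size and scope, and it stands. It does not remove the possible gain in precision. Secondary outcomes have no planned analysis free of the shared slope, and the worst-case price of the split is small.

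**Conclusion.** The point holds as an inexpensive improvement in precision; it is not an error that invalidates any planned estimate. Under assumed person, visit and noise components with 20 people, splitting the baseline takes the SD of the contrast from about no change to a reduction of about 25% with the SAP's random terms as written. The reduction is larger, up to about 40% in the most extreme setting (ratio 0.60), if a visit-level random intercept is also fitted. The gain is greatest for measures that are stable between people and have little day-to-day carry-over. It vanishes when the two slopes are close.

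The primary glucose model has the same form. If a high fasting glucose persists through the visit, which is plausible but not shown in the documents, little changes there either way.

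**What to change.** For secondary and exploratory outcomes with a time-0 value at both visits, replace the single baseline covariate with two: the participant's mean time-0 value and the visit's deviation from that mean. This covers the blood markers, and other outcomes only if a pre-drink value was taken. It does not cover buffet intake, or a gastrointestinal score taken only at 30 minutes.

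State the rule for incomplete baselines:

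- Participant with one visit: use that visit's baseline as the mean and set the deviation to zero.
- Baseline missing at one of two visits: use the observed baseline as the mean and set the deviation to zero at both visits, instead of imputing the sample mean.

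The cost is one extra covariate built from data already collected, and an SE about 1–3% wider for an outcome whose two slopes are equal. If these models have already been run, the split version can be reported as a labelled sensitivity analysis.
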